## **RISK/BENEFIT ASSESSMENT:**

### **1. Risks:**

The potential risks to participants are detailed as follows:

**Emotional discomfort:** This study involves asking questions about sexual and gender identity, one's thoughts and feelings about one's sexual and gender identity, psychosocial well-being, emotional states, and states of depression and anxiety. It is possible, although unlikely, that reflection in response to these psychosocial questions could result in psychological distress. However, the probability and magnitude of harm or discomfort anticipated in the research are not greater, in and of themselves, than those ordinarily encountered in daily life. To mitigate these risks and discomforts, participants will be informed in the

informed consent form that their participation is voluntary and that they can stop the study at any time without penalty. In addition, participants can choose to interact with the web app as much or as little as they want. The primary possible risk is a perception of burden (either in using the web app or completion of the study surveys), which can easily be addressed by withdrawing from the study or discontinuing use of the web app at any time.

**Psychological distress** is a potential risk to participants during the completion of the surveys and engagement with the experimental content. We will provide participants with contact information for the following crisis hotlines if they experience psychological distress related to participation in the study:

- Trevor Project Lifeline
- Trevor Chat/Trevor Text
- Trans Lifeline
- Crisis Text Line
- National Suicide Prevention Line

All hotlines are available 24 hours a day, 7 days a week.

**Unintended disclosure** is also a potential risk. Data will be protected by extensive confidentiality procedures as described below. Data will be collected confidentially; this will be fully described in the informed consent. We have extensive data procedures already in place to ensure security of the data and information provided by participants:

- Data will be encrypted at all times, from the point of entry into Qualtrics to the point of backup and to analysis. Data will be encrypted using standardized software (e.g., 256-bit, PGP).
- Data will be de-identified and linked by the Study ID to minimize risk of inadvertent disclosure.
- Data will never be released to non-study staff.
- All electronic data sharing will be done only on the secure server.

Study staff will be trained on confidentiality standards, which will include the following points:

- Always maintain anonymity of the participant data.
- Questionnaires are to be linked using the Study ID number.
- Protect the electronic security of all databases.
- Computers that can access electronic data should be physically secured and should be password-protected
- Only authorized persons are to have access to electronic databases.

**Privacy and confidentiality concerns:** Participants' confidentiality (names, email addresses, phone numbers) will be protected, but the possibility remains that their information could be lost or stolen or confidentiality could be breached.

Participants will be reminded at the beginning of each survey to consider their surroundings and the privacy of their device and internet connection. All communication between study staff and participants will not include sensitive information that may reveal their participation in a study about SGM or answers to any of the questions answered in the surveys. There is a possibility that participation in this research study could be disclosed in the following ways:

1. If someone besides the participant sees the control website or experimental web app
2. If someone besides the participant sees an email, text message, or direct message via social media sent from the study team and follows a link to the website/web app or a study survey

The risk of disclosure of participation in a research study through receiving study related emails, text messages, direct messages via social media, interacting with the online surveys, or with the intervention on a participant's device will be minimized in the following ways:

1. Participants must enter a password to first gain access to the website or web app
2. After 10 minutes of inactivity, the website will automatically redirect to [www.google.com](http://www.google.com)
3. Emails, text messages, and direct messages via social media that include links to study surveys will not contain any reference to the nature of the survey or study
4. Participants will be encouraged to delete any text messages received as part of the study to protect them from an unauthorized individual viewing the messages, and to interact with the study application when in private (e.g., turn on screen lock, complete surveys when alone). Participants will be notified of these risks in the consent process.

## **2. Benefits:**

Participants will be asked about sensitive information, yet adequate protections for internet data collection are in place for this study. The main benefit of the proposed study to society is the development of a potentially feasible and acceptable web app that impacts key psychosocial outcomes among SGMY ages 13-19, such as coping self-efficacy and symptoms of anxiety and depression. Participants in the experimental condition may experience improvements in their adaptive cognitive and behavioral coping skills, psychosocial wellbeing, symptoms of depression and anxiety, and greater life satisfaction. Potential benefits for the research far outweigh the risks for the participants. Others will benefit because the study will result in increased knowledge about tools that may help SGMY affirm their identities and cope with minority stress. Therefore, the risk/benefit ratio is favorable.

## **3. Subject Privacy:**

All study activities occur over the internet, with specific precautions taken to support participants' privacy. To minimize the risk of participants feeling uncomfortable about answering personal questions, we will use self-completed online surveys. Participants will input the answer to the question themselves. This format also allows participants to choose where and when they are comfortable completing study questionnaires.

## **4. Subject Confidentiality:**

To minimize risks to confidentiality, we will secure study data with all appropriate physical, electronic, and operational protections. Data will be stored in a physically secure environment. All data files will have encryption and strong password protection. Any identifiable data will be stored on University of Pennsylvania's secure servers or on fully encrypted laptops.

We will collect email addresses so we can reimburse participants for their time (i.e., study incentives) and for internal auditing purposes. To ensure we have sent participants their incentives, we will keep the email addresses in a password-protected file on a password-protected secure server. In addition, we will use participant email, IP address, browser/operating system, and time taken to complete the surveys to flag potential fraudulent/suspicious entries.

Survey and intervention data files will identify participants using study ID numbers, assigned by study staff, which will be unrelated to the participant's name or email address. We will keep a file containing

contact information (i.e., email) and IP addresses separate from survey data. This file will be password-protected and stored within a restricted folder on a secure server. The reason for keeping this personal information is solely administrative (i.e., to ensure that we keep a record of incentive payments, and to verify that fraudulent data collection does not occur (e.g., individuals may seek to falsify information on the web survey in hopes of receiving an incentive more than once).

Online surveys and eligibility screening will take place on an encrypted commercial survey website, Qualtrics. This site has been used by the investigators for numerous online surveys with SGMY with no data security breaches. Access to data will be on a role-based standard; only those study staff who require access to each type of data to complete their study-related roles will be allowed access. All study staff will be trained in security and confidentiality procedures, and will sign a confidentiality agreement before receiving access to any participant data. No participant names or other identifying information appear on data documents or in data files as the contact information will be stored separately. Only designated staff will have access to the data.

All web survey data will be secured using SSL 256-bit encryption. SSL encryption is the standard for all web-based transactions that include any identifiable information, including names, addresses, and credit card numbers.

Participant contact information (name, email address, and phone number) will be destroyed at the end of the study, and will never be associated with the study data collected.

## **5. Protected Health Information**

The following PHI will be collected in this study:

- First name
- City, State, zip code, and equivalent geocodes
- Birth month and year
- Telephone numbers
- Electronic mail addresses
- Internet IP addresses

## **6. Compensation:**

Participants will receive \$30 for the baseline survey and \$40 for completion of the follow-up survey. This compensation is small enough to avoid undue influence, yet sufficiently substantial to compensate for time and effort, and promote retention.

All compensation and incentives will be paid as Amazon.comdigital gift cards. Payment for the baseline survey will be sent once participants have completed the survey and have registered for an account within their respective arm of the intervention. The incentive for the follow-up survey will be sent after the participant completes the associated survey.

## **7. Data and Safety Monitoring:**

The Principal Investigator will provide oversight of all study procedures and quality assurance checks. The data safety and monitoring plan includes the following protocols:

- Electronic files and records will be stored in a firewalled, encrypted server at the University; only research staff will have access to this directory. To ensure participants' safety as well as the data's validity and integrity, only staff with extensive experience in studies with SGMY youth will be hired.
- All staff will have signed a confidentiality agreement. We have several mechanisms to ensure the security and integrity of the data. The intervention content, questionnaires, and personal information will be secured with role-based security that will provide different types of users with different access privileges.
- Survey data and web app data will be located on unique servers. Survey data and web app data will be linked using a unique Study ID.
- All study personnel will have completed the Human Subject Training established by the CITI program. In addition, in compliance with the NIH policy, University graduate students and staff will participate in at least 8 hours of mandatory case study and discussions regarding scientific integrity and human subjects. Any additional personnel who may join the project will complete this training before they handle any subject data.
- All research staff will be trained to recognize and document any unusual events or circumstances that occur during the study. Staff will be trained to immediately report any adverse events to the Principal Investigator and the University IRB.
- The Principal Investigator and Project Director will monitor staff closely. Staff deficient in any aspect of performance will be re-trained, closely monitored for proficiency, and if not adhering to established protocols and procedures, will be terminated.
- The Principal Investigator will be responsible for dissemination of study findings through presentations and publications. The Principal Investigator will also be solely responsible for handling any requests from other investigators to examine the data collected during this study.

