## **METHODS:**

### **1. Study Instruments:**

Participants will complete two online surveys during the trial (baseline and a follow-up survey on Day 28). Assessments will take 30-40 minutes to complete. Assessment measures fall into four categories: 1) psychological targets, 2) psychosocial wellbeing and mental health, 3) intervention acceptability and satisfaction, and 4) demographics and other baseline assessments.

Psychological Targets. The immi web app is designed to 1) affirm SGM identities, 2) promote a sense of connectedness to the SGM community, and 3) teach adaptive cognitive and behavioral coping skills. Aligned with our theory of change, we will measure psychological targets that map onto each of these three constructs at baseline and at follow-up.

Specifically, to measure change in SGM identity related constructs, we will administer the identity affirmation subscale from Lesbian Gay and Bisexual Positive Identity Measure. We will also administer the concealment motivation, internalized homonegativity, and acceptance concerns subscales of the Lesbian Gay and Bisexual Identity Scale. A single item measure of 'outness' to friends and family will be included to assess change in willingness to disclose one's SGM identity.

---

 Riggle, E. D., Mohr, J. J., Rostosky, S. S., Fingerhut, A. W., & Balsam, K. F. (2014). A multifactor lesbian, gay, and bisexual positive identity measure (LGB-PIM). *Psychology of Sexual Orientation and Gender Diversity*, 1(4), 398-411.

 Mohr, J. J., & Kendra, M. S. (2011). Revision and extension of a multidimensional measure of sexual minority identity: The Lesbian, Gay, and Bisexual Identity Scale. *Journal of counseling psychology*, 58(2), 234-245.

 Quinn, D. M., Williams, M. K., Quintana, F., Gaskins, J. L., Overstreet, N. M., Pishori, A., ... & Chaudoir, S. R. (2014). Examining effects of anticipated stigma, centrality, salience, internalization, and outness on psychological distress for people with concealable stigmatized identities. *PLoS one*, 9(5), e96977.

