Appropriateness Scale. We will assess the perceived usability of the web app with the Systems Usability Scale. A measure of intervention satisfaction and suggestions for intervention improvement that was created in-house for the purpose of this study will also be included. This measure consists of multiple choice questions (e.g. 'How would you rate your overall experience of this product?' (1 = excellent to 7 = very bad) and free text responses (e.g. How could this product be more helpful to you? [text box]). We will measure intervention exposure using paradata from the intervention, including counts of user sessions, session lengths, and pages visited.

**Demographics and other baseline assessments.** To describe our sample and examine whether the experimental and control groups differ on any key demographic characteristics at baseline, we will include standard demographic measures (e.g. age, race, ethnicity etc.) as well as measures of gender identity, sexual orientation, preferred pronouns, sex assigned at birth, educational attainment, educational status, socioeconomic status, and living situation. To characterize our sample and to examine whether the effects of the intervention differ for adolescents experiencing differing levels of minority stress, we will include a short version of the Sexual Minority Adolescent Stress Inventory at baseline. We will also include a measure of mental health and other affirmative LGBTQ+ resources accessed in the last 12 months at baseline to better characterize the degree to which our sample already has access to supportive resources (adapted from McInroy et al. 2019 & the Trevor Project, 2021).

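### Distress from the surveys and app is a named risk, but no question about it is described for either arm, so zero spontaneous reports would say little about harm

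*Combined protocol and SAP*

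**What the plan says.** Under Risk/Benefit Assessment, 1. Risks, the protocol states that psychological distress "is a potential risk to participants during the completion of the surveys and engagement with the experimental content". The planned response is a list of external services: "We will provide participants with contact information for the following crisis hotlines if they experience psychological distress related to participation in the study". No report back to the study is described.

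Detection is covered in 7. Data and Safety Monitoring: "All research staff will be trained to recognize and document any unusual events or circumstances that occur during the study", and "Staff will be trained to immediately report any adverse events to the Principal Investigator and the University IRB". Other ways in which staff could learn of an event are also passive:

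- the withdrawal email address (5. Early Withdrawal of Subjects);
- the consent-form invitation to make contact with questions, and phone or email contact to end participation (Informed Consent, 1. Consent Process);
- notification of certain institutional admissions (Methods, 6. Subject Follow-up).

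On the setting, 3. Subject Privacy says: "All study activities occur over the internet, with specific precautions taken to support participants' privacy". There are two scheduled surveys, at baseline and Day 28.

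On content, Methods, 1. Study Instruments says: "Assessment measures fall into four categories: 1) psychological targets, 2) psychosocial wellbeing and mental health, 3) intervention acceptability and satisfaction, and 4) demographics". Both arms complete perceived stress, GAD-7, PHQ-8, PANAS-C and shame and guilt scales at both time points. Acceptability is reported by the experimental group only, and under that heading: "A measure of intervention satisfaction and suggestions for intervention improvement that was created in-house for the purpose of this study will also be included". Free-text boxes are part of it. According to Study Design, reminders to use the assigned resource go to the experimental arm and not to the control arm.

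Study Procedures, 5. Statistical Analysis compares the arms on each construct by intention to treat, adjusting for baseline. It plans no harm summary by arm.

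**The concern.** The plan names a harm but does not describe asking anyone whether it occurred. In a self-completed online trial, staff do not see participants, so training them to recognise events gives them little to recognise. What reaches them depends on who chooses to write in or who is reported by someone else.

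Two consequences follow. First, a final report with few or no adverse events could mean little harm or little capture, and nothing in the plan would tell these apart. Second, free-text feedback and engagement reminders are described for one arm only, so incidental reports could differ by arm for reasons unrelated to harm.

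The symptom scales cover part of the gap. They do not link a change to participation, they are compared only as mean change, and they miss distress that resolves before Day 28 or leads to dropout. The participants are aged 13 to 19, and a waiver of parental consent is requested for those under 18, so informative harm data are worth a small effort.

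**Working it through.** **Inputs from the protocol.** 300 randomised 1:1, so 150 per arm; a loss allowance of up to 35%; about 97 per group after loss; a retention target of at least 80%.

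**The plan's own figure.** 300 × (1 − 0.35) / 2 = 97.5, which agrees with the stated figure of about 97 per group. This is the efficacy sample size; the documents give no figure for harm. At 80% retention the number is 150 × 0.80 = 120 per arm.

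**Assumptions (not in the documents).** A true rate *r* of study-related distress in an arm, and a probability *s* that a case reaches staff without being asked about. Cases are treated as independent.

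**Step 1: chance of no report when distress is present.** P(0 reports) = (1 − *r* × *s*)^150.

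| Share of cases reaching staff (*s*) | *r* = 5% | *r* = 10% |
|---|---|---|
| 100% | 0.05% | <0.01% |
| 50% | 2.2% | 0.05% |
| 20% | 22% | 4.8% |
| 10% | 47% | 22% |
| 5% | 69% | 47% |

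For example, with *r* = 5% and *s* = 10%: (1 − 0.005)^150 = 0.47, and the expected number of reports is 150 × 0.05 × 0.10 = 0.75.

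**Step 2: what zero spontaneous reports would exclude.** The one-sided 95% upper bound for zero events in *n* is 1 − 0.05^(1/*n*). For *n* = 150 it is 1.98%, and it applies to *r* × *s*. The bound on *r* is therefore 1.98% / *s*: 4.0% at *s* = 50%, 9.9% at 20%, 19.8% at 10% and 39.5% at 5%.

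**Step 3: what asking directly would exclude.** If everyone asked answers truthfully and none reports distress:

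- *n* = 120: 1 − 0.05^(1/120) = 2.5%;
- *n* = 97: 1 − 0.05^(1/97) = 3.0%.

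At *r* = 5%, the expected number of positive answers is 120 × 0.05 = 6, or 97 × 0.05 = 4.9. These bounds describe completers only. Per arm, 150 − 120 = 30 or 150 − 97 = 53 participants would not have been asked.

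**Step 4: what the mean comparison shows.** If a fraction *q* of an arm worsens by *k* points and the same fraction improves by *k*, the mean change is *qk* − *qk* = 0. A net shift would be visible in the planned analysis, but offset individual worsening would not.

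**Step 5: limits of a worsening table.** With assumed worsening rates of 10% and 20% and two-sided 0.05, power is about 50% at 97 per arm and 58% at 120. The table would describe harm with useful precision but would not be a powered test.

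**The case against.** The strongest reply is that distress is measured. Both arms complete several validated distress scales at baseline and week 4, and the main analysis compares them by arm in either direction. That stands. A reader might infer that neither arm is asked about distress, or that harm cannot be compared between arms. The documents support neither: what is missing is attribution to participation and any analysis of the scales as harms.

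Other points also stand, in part:

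- Participants can contact staff. These routes are real, but they depend on the participant's initiative and are framed around questions or withdrawal.
- A reader might infer that adverse events will come mainly from the experimental arm. The documents show only that feedback boxes and engagement reminders differ by arm. Consent-form contact and the reminders to complete the follow-up survey are not limited to one arm, so a difference in reporting is possible but not established.
- A reader might infer that the favourable risk/benefit statement rests on adverse event counts. It is a prospective judgement for the IRB in a study classed as minimal risk, and no objective makes a safety claim.
- The survey instruments, consent form and SOPs are not reproduced, so an undescribed harm item cannot be excluded. If one exists, the protocol should say so and state how it will be reported.
- A Day-28 item misses participants who have left. This is correct, and the fix has to allow for it.

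**Conclusion.** The point holds as a gap in harm ascertainment; it is not a flaw in the efficacy comparison. A named risk has no described participant-facing question in either arm, and passive capture in an online trial makes zero reports weak evidence.

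The size depends on a capture rate that the documents do not give. If 5% of 150 were affected, the chance of no report runs from 0.05% with full capture to 69% when one case in twenty reaches staff. If capture were high, the concern would largely disappear, but nothing in the plan makes high capture likely or measurable. Direct questioning with no positive answers would bound the rate among completers below 2.5% (n = 120) or 3.0% (n = 97), assuming candid answers. It is a worthwhile, low-cost improvement.

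**What to change.** 1. Add to the Day-28 survey, worded identically in both arms, a short item on whether the surveys, website or app caused distress at any time during the four weeks, and how severe it was. Report the answers by arm with confidence intervals.
2. From the PHQ-8 and GAD-7 data already planned, tabulate by arm the number who worsened from baseline by a margin fixed before data review. Present this as descriptive.
3. Show discontinuations, with reasons where known, and non-completion of the Day-28 survey by arm in the same table, because the new item cannot reach those who drop out.
4. State in the protocol that spontaneous reports will be listed by arm and by route of receipt, and that a low count will not be read as absence of harm.

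The cost is a slightly longer survey (now 30 to 40 minutes), one extra table and an IRB amendment. A direct question will also draw some non-specific complaints; because it is put identically to both arms, the comparison between arms remains interpretable.
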